A group of 24 patients previously treated in the Riley NICU from the years 2016 – 2017 will be used as a historic control cohort. Historic patients will be eligible for enrollment in the study if they have one of the above listed diagnoses, received post-operative parenteral nutrition, and were treated with soy-based lipid at standard dosing (2-3 g/kg/day). Historic patients will be ineligible to participate if any of the above listed exclusion criteria are true at the time of their abdominal surgery. Historic patients will be matched to prospective patients when able. This matching will first utilize in order: 1. days of parenteral lipid therapy, 2. diagnosis, 3. birth gestational age, and 4. birth weight when selecting for inclusion.

Study Procedures

1. Smoflipid® (20% lipid emulsion) treatment group
 - a. Advancement:
 - i. Smoflipid will be started at 1 g/kg/d on day 1 of parenteral nutrition after enrollment and advanced by 1 g/kg/d each subsequent day to a goal maximum of 3 g/kg/d
 - b. Maintenance and weaning [8]:
 - i. The Table below will be used as a guide for weaning Smoflipid as enteral nutrition is initiated and advanced.
 - ii. Patients will continue to be monitored by a clinical dietitian and pharmacist as per standard of care. Pending their recommendations, along with the clinical state of the child, the actual dose of Smoflipid needed may vary by individual patient.
 - c. Other parenteral nutrition components
 - i. Amino acid will be provided to meet estimated protein requirements only and will not be increased as a form of caloric intake.
 1. Term infant approximate goal of 3 g/kg/day and preterm infant approximate goal of 3.5 – 4 g/kg/day.
 - ii. Glucose infusion will be utilized and advanced per standard protocol to provide remainder of estimated non-protein caloric need of each individual patient.
 1. Maximum glucose infusion rate (GIR) while enrolled in study of 16 mg/kg/min. If further caloric intake is required, Smoflipid will be increased to a maximum of 3 g/kg/d.

Table 1: Smoflipid dosage recommendations for weaning as enteral feeds advanced

% calories from PN	Volume enteral feeds (ml/kg/d)	Enteral calories (kcal/kg/d)	Lipid (g/kg/d)
80-100%	\leq 20-40	\leq 30	3
60-80%	40-60	30-40	3
50-60%	60-80	40-50	2.5
40-50%	80-100	50-60	2
30-40%	100-110	60-70	1.5
20-30%	120	70-90	1
<20%	>120	>90	0

2. Intralipid® (20% lipid emulsion) reduction treatment group
 - a. Advancement:
 - i. Intralipid:

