 - i. Each patient's chart will be reviewed for documentation of retinopathy of prematurity or bronchopulmonary dysplasia (chronic lung disease). The absence or presence of these diseases at the time of discharge will be noted for each study patient, particularly those patients born prematurely at less than 37 weeks gestation.
- d. Length of Stay:
 - i. An ICU length of stay will be calculated for each patient based on their admit date and discharge date from the Riley NICU.
 - ii. For patients transferred to another unit prior to discharge the transfer date will also be documented. For these patients a NICU length of stay and total hospital length of stay will be calculated.
- e. Laboratory monitoring (see Table 2 below for reference schedule):
 - i. Effort will be made to draw all study lab tests along with other standard of care, routinely scheduled labs.
 - ii. The schedule outlined here is a schedule of minimum laboratory work to be obtained. These studies may be obtained more often by the patient's primary clinical team. Any lab test obtained by the primary team within 3 days for weekly labs or within one week for less frequent labs will be used in place of the research lab test.
 - iii. Of note all lab tests listed could be considered standard of care, with the exception of INR.
 - iv. Essential fatty acid profiles will be obtained every 4 weeks (28 days) while receiving study lipid regimen.
 - 1. Blood volume needed 0.3-1mL
 - 2. Considered standard of care in any patient on alternative lipid dosing, such as patients enrolled in this study.
 - 3. If diagnosed with essential fatty acid disorder, defined as triene:tetraene ratio >0.05:
 - a. If Smoflipid dose is less than 3 g/kg/d, SMOF will be increased by 0.5 g/kg/d or to 3 g/kg/d maximum
 - b. Those receiving Smoflipid at 3 g/kg/d will be changed to Intralipid at current Smoflipid dose
 - c. Those receiving Intralipid will have their dose increased by 0.5 g/kg/d to maximum of 3 g/kg/d
 - v. Total and fractionated bilirubin levels will be monitored at least once weekly (7 days)
 - vi. Liver function panel and gamma-glutamyl transferase (GGT) will be monitored at least every 2 weeks (14 days).
 - vii. Triglyceride levels will be monitored within the first 48 hours of lipid initiation and then once weekly (7 days).

1. If triglyceride level >250 mg/dL will decrease dose of study lipid by 1g/kg/d to minimum of 2 g/kg/d of Smoflipid or 1 g/kg/d three days per week for Intralipid

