2. Lipid infusion will be held if triglyceride level > 400 mg/dL
 - a. Once triglyceride level <400 mg/dL lipid infusion can be restarted. A lower dose can be used if deemed necessary by the primary care team and dietitian.

viii. Bleeding studies

1. Platelets will be monitored once weekly until stable (minimum 2 consistent values, 5-7 days apart) and then once every 4 weeks.
2. INR will be measured once weekly until stable (at least 2 consistent values, 5-7 days apart) and then once every 4 weeks.
 - a. Blood volume 1.7 mL
 - b. Because this lab is not standard of care, the cost will be covered by research funds, not by the individual patient.

ix. Glucose will be monitored at initiation of parenteral nutrition until stable and then with significant changes in glucose infusion rate. This can be performed via basic metabolic profile (BMP), point of care (POC) glucose, or any other lab source that provides a blood glucose measurement.

1. If the blood glucose is >200 mg/dL on more than one measurement separated by at least 3 hours, the primary team will consider decreasing the patient's GIR.
2. If blood glucose is <50 mg/dL the primary team will consider increasing the GIR.

x. Blood volume:

1. Minimum blood volume per each phlebotomy event are listed in Table 2.
2. Total minimum blood volume 24.4 mL per patient over the 14 blood draws during the study.

xi. Post-study monitoring:

1. As indicated in Table 2, triglyceride, hepatic function panel, GGT, essential fatty acid panel, platelet count, and INR will be measured 2-3 weeks post-study completion or at time of discharge, whichever comes first.
 - a. This time frame will be for all patients enrolled in the study, regardless of their length of time within the study.
 - b. If the patient is to be discharged from the hospital prior to this 2-3 week time period, labs will be drawn within 3 days of discharge, prior to leaving the hospital.

Table 2: Minimum laboratory requirements while enrolled in study (TG= triglyceride, HFP = Hepatic Function Panel, FB = fractionated bilirubin, GGT= gamma glutamyl transferase, EFA = essential fatty acids, PLT= platelet count) (Blood volume is minimum required to perform all tests listed)

	Week													
	0	1	2	3	4	5	6	7	8	9	10	11	12	+2-3
Test	TG	TG	TG	TG	TG	TG	TG	TG	TG	TG	TG	TG	TG	TG
	HFP	FB	HFP	FB	HFP	FB	HFP	FB	HFP	FB	HFP	FB	HFP	HFP
	GGT		GGT		GGT		GGT		GGT		GGT		GGT	GGT
					EFA				EFA				EFA	EFA
	PLT	PLT			PLT			PLT					PLT	PLT
	INR	INR		INR			INR				INR		INR	INR

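### The triglyceride rule and the Smoflipid advancement rule are not reconciled: read literally, a first-check level of 251-400 mg/dL is followed by a rise to 3 g/kg/d

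*Combined protocol and SAP*

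**What the plan says.** All references are to the combined protocol and SAP.

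- **Advancement (Study Procedures 1.a).** The Smoflipid schedule reads: "started at 1 g/kg/d on day 1 of parenteral nutrition after enrollment and advanced by 1 g/kg/d each subsequent day to a goal maximum". The ceiling is 3 g/kg/d. No triglyceride condition is attached.
- **Increase for calories (1.c.ii.1).** Following the limit on glucose infusion: "If further caloric intake is required, Smoflipid will be increased to a maximum of 3 g/kg/d". This rule has no triglyceride condition either.
- **Timing of checks (3.e.vii).** "Triglyceride levels will be monitored within the first 48 hours of lipid initiation and then once weekly (7 days".
- **Reduction (3.e.vii.1).** "If triglyceride level >250 mg/dL will decrease dose of study lipid by 1g/kg/d to minimum of 2 g/kg/d of Smoflipid". The same sentence gives the Intralipid arm a different minimum: 1 g/kg/d on three days a week.
- **Hold (3.e.vii.2).** "Lipid infusion will be held if triglyceride level > 400 mg/dL".
- **Discretion.** Under Maintenance and weaning (1.b.ii), "the actual dose of Smoflipid needed may vary by individual patient" on dietitian and pharmacist advice. On the laboratory schedule (3.e.ii), "These studies may be obtained more often" by the primary team.
- **Other uses of 250 mg/dL.** Levels above it exclude an infant at enrollment. Persistent levels above it on three or more draws, despite a decreased or held dose, are an individual stopping criterion (Criteria for Stopping Study, 1.b.vi). Table 3 grades 250-500 mg/dL as a moderate (Grade 2) adverse event.

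**The concern.** The early check shows how an infant handles the first lipid. In the Smoflipid arm it is scheduled while the dose is at or below the floor of the only rule that responds to 251-400 mg/dL. Followed to the letter, two written rules then treat the same level in opposite ways: at 300 mg/dL an infant on 3 g/kg/d goes down to 2, while an infant on 2 goes up to 3. The Intralipid arm does not have this problem, because it starts at 1 g/kg/d and has a written step below that.

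What is at stake is several days of lipid at a dose that the protocol itself treats as too high for that level, in surgical neonates, and inconsistent handling between clinicians who read the rule differently. The 2 g/kg/d floor is a sponsor choice and is not questioned. Doses during weaning fall under the written discretion and are not part of this point.

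**Working it through.** The plan states no figure to reproduce, so the check applies its rules day by day.

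**Inputs.** Scheduled dose on day k: d = min(3, k) g/kg/d (1.a). Target above 250 mg/dL: t = max(2, d - 1); reduction = max(0, d - t) (3.e.vii.1). Hold above 400 mg/dL (3.e.vii.2). First check on day 1 or 2, then weekly (3.e.vii).

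**Rule at each scheduled dose, level 251-400 mg/dL**

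| Day | Scheduled dose | Target | Written reduction |
|---|---|---|---|
| 1 | 1 | 2 | 0 |
| 2 | 2 | 2 | 0 |
| 3 onward | 3 | 2 | 1 |

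The reduction is zero throughout the first-check window and becomes 1 g/kg/d only once the dose has reached 3.

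**Excess over a cap at 2 g/kg/d, level found on day 2.** The next scheduled check is day 8 if the week runs from lipid start, or day 9 if it runs from the first check.

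1. *The cut applies to the dose at the draw and is not revisited until the next check.* Days 3-7: 5 x 3 = 15 against 5 x 2 = 10, excess 5 g/kg. Days 3-8: 6 x 3 = 18 against 6 x 2 = 12, excess 6 g/kg.
2. *The cut applies to the dose running when the result is acted on, during day 3.* Excess at most 3 - 2 = 1 g/kg.
3. *The cut applies to the upcoming day-3 dose.* 3 - 1 = 2, excess 0.

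Readings 2 and 3 assume that the dose then stays at 2 until the next check. Under reading 1, each day of earlier action removes 1 g/kg.

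**Level found on day 1, reading 1, next check day 8.** Days 2-7: 2 + 5 x 3 = 17 against 6 x 2 = 12, excess 5 g/kg.

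**The case against.** The strongest reply is that the reduction rule is not limited to the dose running at the draw and does not lapse after one look. If the latest known level is 300 mg/dL and the dose becomes 3, the condition is still met and the target is 2. On that view the excess is 0 or at most 1 g/kg. This is a fair reading, and it rules out saying flatly that the protocol takes no action or sends such infants to 3 g/kg/d for a week. A reader might infer that from the schedule, but the documents leave it open. What stands is that nothing in the text chooses between the readings.

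The second reply is that safeguards exist. Infants above 250 mg/dL at enrollment are excluded, so the gap needs a rise to 251-400 on only 1-2 g/kg/d. Clinicians can redraw, adverse events are monitored daily, and dosing can be individualised. On the literal path, the next check cuts an infant on 3 who is still above 250 to 2. All of this is true and keeps the point small. But none of these provisions sets a dose for this range during advancement, and the individual-dosing text sits under Maintenance and weaning.

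The third reply concerns the remedy. Freezing an infant at whatever dose is running would hold one found on day 1 at 1 g/kg/d, below the 2-3 g/kg/d that defines the arm. A blanket ban on increases would also collide with the essential fatty acid rule (3.e.iv.3.a), which raises Smoflipid by 0.5 g/kg/d when the dose is below 3. Both objections are right, and the fix is framed to avoid them.

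**Conclusion.** The point holds as an unreconciled pair of rules, at minor severity. For a first-check level of 251-400 mg/dL, the excess over a cap at 2 g/kg/d before the next scheduled check is 0, at most 1, or 5-6 g/kg, according to which dose the cut is taken to govern. The top of that range assumes the most literal reading, no extra draw and no discretionary change, so it is not an expected value.

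A reader might go further and infer harm to infants or a distorted comparison of cholestasis. The documents do not support either: they give no frequency for this level at the first check, and no effect on the primary endpoint is claimed. Nor does the point require a change to the stopping criterion for persistent hypertriglyceridemia.

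**What to change.** Add to Study Procedures 1.a, 1.c.ii.1 and 3.e.vii that, during advancement and for increases made for calories, Smoflipid is not raised above 2 g/kg/d while the most recent triglyceride level exceeds 250 mg/dL, and that an infant on 1 g/kg/d may still advance to 2. State that the increase for essential fatty acid deficiency (3.e.iv.3.a) is unchanged. Leave the 2 g/kg/d floor and stopping criterion 1.b.vi as written.

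The cost is protocol wording, with no extra patients or tests. The clinical downside is up to 3 - 2 = 1 g/kg/d less lipid until the level falls, the same reduction that the protocol already accepts when it cuts 3 to 2. Glucose is already used "to provide remainder of estimated non-protein caloric need of each individual patient", up to an infusion rate of 16 mg/kg/min (1.c.ii).

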2. Secondary (comparison of each listed parameter between the prospective treatment groups in addition to comparison of each treatment group with historic controls):
 - a. Growth (rate of change)

- i. Weight, length, and head circumference at enrollment, on a weekly basis while receiving study lipid, and 2-3 weeks post-study lipid completion.
- ii. Weight, length, and head circumference at 36 weeks corrected gestational age and time of discharge.
- b. Essential fatty acid profile differences and development of deficiency
- c. Average total caloric intake for all patients on weekly basis
 - i. Average lipid dose delivered on weekly basis
- d. Feeding tolerance/ percentage of total calories from enteral feeds
 - i. Time to achievement of enteral autonomy (full enteral feedings)
 - ii. Percentage of enteral calories at end of study
 - iii. Percentage of patients in each group with enteral autonomy
- e. Transaminase, alkaline phosphatase, GGT levels at enrollment, every 4 week time point, and end of study
- f. Triglyceride concentration at baseline, weekly, and end of study
- g. Rates of other diagnoses in each study group
 - i. Retinopathy of prematurity as diagnosed by Ophthalmologic examination
 - ii. Chronic lung disease as defined by need for oxygen at time of discharge or 36 weeks corrected gestational age (if at least 28 days of age), whichever comes first.
- h. Rates of adverse and serious adverse events in each group
- i. Length of stay
- j. Two year neurodevelopmental differences using ASQ-3 screening

Study Population

Inclusion criteria

Infants admitted to the Riley Hospital Neonatal Intensive Care Unit (NICU), regardless of postmenstrual or corrected gestational age, with anticipated need for parenteral nutrition for four or more weeks PLUS one or more of the additional inclusion criteria listed below will be eligible for inclusion within the study and for randomization. Inclusion criteria include:

- Anatomic intestinal defect: Neonate with intestinal atresia, omphalocele, gastroschisis or volvulus with or without intestinal resection and need for parenteral nutrition pre or post-operatively.
- Ischemic/perforation intestinal injury: Neonates with spontaneous intestinal perforation or necrotizing enterocolitis requiring surgical intervention with need for parenteral nutrition post-operatively.

Exclusion criteria at time of study enrollment

- Infant with current weight less than 750 grams

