 1. Intralipid will be started on day 1 of parenteral nutrition at 1g/kg/d

2. Intralipid dose will be maintained at 1g/kg/d while enrolled in the study and receiving parenteral nutrition, unless other clinical concerns arise as documented by primary team.
 - a. If further caloric intake is required, Intralipid may be increased at the discretion of the treating faculty based on the needs of the individual patient.
- ii. Other parenteral nutrition components:
 1. Amino acid will be provided to meet estimated protein requirements only and will not be increased as a form of caloric intake.
 - a. Term infant approximate goal of 3 g/kg/day and preterm infant approximate goal of 3.5 – 4 g/kg/day.
 2. Glucose infusion will be utilized and advanced per standard protocol to provide remainder of estimated non-protein caloric need of each individual patient.
 - a. Maximum glucose infusion rate (GIR) while enrolled in study of 16 mg/kg/min. If further caloric intake is required, Intralipid will be increased at the discretion of the treating faculty based on needs of the individual patient.
3. All Study Patients:
 - a. Enteral feedings:
 - i. Enteral breast milk or formula choice will be at the discretion of the primary faculty physician and advanced per physician practice.
 - b. Anthropometric Measurements:
 - i. Each group will have growth monitored per standard protocol with daily weights and weekly head circumference (OFC) and length.
 - ii. Weekly measurements used for research purposes will include weekly weight, length, and OFC as documented directly by the research team (primary investigators or same registered dietician).
 - iii. Corrected measurements will also be documented with weight, length, and OFC documented at 36 weeks (+/- 3 days) corrected gestational age.
 - iv. Follow-up measurements at 2 – 3 weeks after stopping study lipid or time of discharge, whichever comes first.
 - v. At each time point, anthropometric measurements will be replicated in triplicate and the average value for that measurement will be reported within the study.
 - vi. In the event of safety concerns to the patient or research team, as raised by the research team, patient care team, or regulatory entities, the study measurements will be conducted by the bedside patient nurse. These measurements will include length board use.

- c. Diagnoses associated with Prematurity:

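### Required glucose testing follows infusion-rate changes, which the assigned lipid dose influences, with no common schedule, so glycaemic adverse events may be ascertained unequally between arms

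*Combined protocol and SAP*

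**What the plan says.** The glucose rule is in Study Procedures 3.e.ix: "Glucose will be monitored at initiation of parenteral nutrition until stable and then with significant changes in glucose infusion rate". Neither *stable* nor *significant* is defined there. For platelets and INR, item 3.e.viii does define stability (at least two consistent values, 5-7 days apart) and then sets a four-weekly draw.

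Table 2 is titled "Minimum laboratory requirements while enrolled in study (TG= triglyceride, HFP = Hepatic Function Panel, FB = fractionated bilirubin" and goes on to list GGT, essential fatty acids and platelets; INR also has a row. Glucose appears in no week. Item 3.e.ii qualifies the whole schedule: "The schedule outlined here is a schedule of minimum laboratory work to be obtained", and "These studies may be obtained more often by the patient's primary clinical team".

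The infusion rate is tied to the lipid strategy. Smoflipid is "advanced by 1 g/kg/d each subsequent day to a goal maximum of 3 g/kg/d" and then weaned by Table 1. In the other arm, "Intralipid dose will be maintained at 1g/kg/d while enrolled in the study and receiving parenteral nutrition", with increases allowed at clinical discretion. The glucose wording is the same in both arms: "Glucose infusion will be utilized and advanced per standard protocol to provide remainder of estimated non-protein caloric need of each individual patient", with the same 16 mg/kg/min ceiling. Criteria for Stopping Study 1.b.v recognises that lipid reduction may call for a raised infusion rate.

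Table 3 grades hyper- and hypoglycaemia. Study Objectives 2.h lists "Rates of adverse and serious adverse events in each group" as a secondary comparison. Statistical Considerations uses Fisher's exact test at 5% for categorical variables. The trial is unblinded.

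**The concern.** The chance of recording an abnormal glucose value depends on how often glucose is measured. Once values are stable, the protocol-required measurements follow a variable that the randomised treatment changes. Two arms with the same true glycaemic risk could then show different event rates, and a true difference could be exaggerated or hidden.

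The plan offers no way to separate the two explanations. It has no glucose series sampled alike in both arms and does not report the number of tests. Daily adverse-event surveillance does not help, because it does not require a glucose reading. Persistent hyperglycaemia is also an individual stopping criterion (1.b.v), so unequal testing could affect withdrawals as well. A pilot meant to find design flaws before a larger trial should be able to read this signal.

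**Working it through.** The plan states no number of glucose checks, no number of rate changes and no glycaemic event rate, so there is no figure to reproduce. The checks below are illustrations. Energy values, calorie needs, check counts and risks per check are assumptions, not taken from the documents.

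**1. Does the assigned arm move the infusion rate?** Extra rate = lipid gap (g/kg/d) × kcal per g lipid ÷ kcal per g dextrose × 1000/1440. Assume lipid at 9-10 kcal/g and dextrose at 3.4-4.0 kcal/g.
- Gap of 2 g/kg/d (3 versus 1): lowest 2 × 9/4.0 × 1000/1440 = 3.1; highest 2 × 10/3.4 × 1000/1440 = 4.1 mg/kg/min.
- Gap of 1 g/kg/d: 1.6 to 2.0 mg/kg/min.

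A higher *level* in the reduction arm therefore follows from the design.

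**2. Does it move the number of significant changes?** In the middle rows of Table 1, each 10 kcal/kg/d gain in enteral calories comes with a 0.5 g/kg/d fall in Smoflipid, about 5 kcal/kg/d at 10 kcal/g. Lipid absorbs about half the step. If reduction-arm lipid stays at 1 g/kg/d, glucose absorbs all of it:
- Reduction arm: 10/3.4 × 1000/1440 = 2.04 mg/kg/min per step.
- Smoflipid arm: 5/3.4 × 1000/1440 = 1.02 mg/kg/min per step.

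Next, step through all seven Table 1 rows, using 15, 35, 45, 55, 65, 80 and 95 kcal/kg/d for enteral calories (E). Rate = (T − E − 10L − 4P(T−E)/T)/3.4 × 1000/1440, kept within 0-16. T is total need (90-120 kcal/kg/d), L is lipid, and P is protein (3-4 g/kg/d, scaled down as PN falls). Reduction-arm lipid is taken as 1 g/kg/d until the last row, then 0. Number of changes, reduction versus Smoflipid:
- Any change: equal, 5-6 in each arm.
- Changes of at least 1 mg/kg/min: 5 versus 2.
- Changes of at least 2 mg/kg/min: 2 versus 1.

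The counts are sensitive to assumptions. With protein fixed at 12 kcal/kg/d (3 g at 4 kcal/g) and T = 110, the reduction-arm steps are 4.08, 2.04, 2.04, 2.04, 3.06 and 1.02. The Smoflipid steps are 4.08, 1.02, 1.02, 1.02, 2.04 and 1.02. That gives 6 versus 6 at a threshold of 1, and 5 versus 2 at a threshold of 2. In these scenarios the reduction arm never has fewer changes, but the size of the difference depends on what *significant* means.

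**3. What could unequal checking do?** With the same true risk q per check in both arms, the share of infants with at least one abnormal value after m checks is 1 − (1 − q)^m. Fisher rejection is by exact enumeration, two-sided 5%, 25 per arm.

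| q | Checks, Smoflipid v reduction | Infants with an abnormal value | Fisher rejects |
|---|---|---|---|
| 2% | 10 v 10 | 18% v 18% | 2.2% |
| 2% | 10 v 15 | 18% v 26% | 5.2% |
| 2% | 10 v 20 | 18% v 33% | 13.6% |
| 2% | 20 v 24 | 33% v 38% | 3.8% |
| 5% | 10 v 10 | 40% v 40% | 3.0% |
| 5% | 10 v 15 | 40% v 54% | 12.0% |
| 5% | 10 v 20 | 40% v 64% | 33.5% |
| 5% | 20 v 24 | 64% v 71% | 4.3% |

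The effect runs from slight, when a few extra checks sit on a large common base, to large, when the number of checks doubles. The formula counts any single abnormal value, so it mainly describes grade 1 events. The glucose-range criteria for grade 2 and 3 hyperglycaemia need two determinations 6 hours apart, and grade 2 hypoglycaemia needs repeated measures.

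**The case against.** The strongest reply is that the plan does not say the reduction arm will have more rate changes. It says only that a higher rate may be needed. The glucose wording and ceiling are the same in both arms, and Smoflipid has steps of its own, up and down, that can move the rate. This stands: more checks by design is an inference.

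A reader might also infer that glucose is tested only when the rate changes. The documents do not support that. Testing runs until stable in both arms, which may cover most early upward steps, and the schedule is a minimum. Extra testing does not restore balance by rule, however, because clinicians who know the arm decide on it.

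Nor is glucose the only graded laboratory event without calendar draws. Creatinine, haematocrit and neutrophils are graded in Table 3 and absent from Table 2. What sets glucose apart is that its written trigger is linked to the assigned treatment.

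Finally, it is tempting to call glucose intolerance the main expected harm of lipid reduction. The protocol lists hyperglycaemia among several stopping abnormalities without ranking it, and its background stresses growth and neurodevelopment.

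**Conclusion.** The point holds as a risk of unequal ascertainment that the plan does not address. After the until-stable period, required glucose testing depends on a rate that the assigned lipid dose influences, no common schedule exists, and glycaemic events feed a between-arm comparison in an open-label trial.

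More checking in the reduction arm is plausible from the Table 1 steps (about 2 versus 1 mg/kg/min per mid-wean step at 10 and 3.4 kcal/g). The documents do not establish that it will happen. The size is unknown: every check count and risk above is assumed, and the result moves with the undefined threshold and with the amount of testing common to both arms. A reader should not conclude that an excess of glycaemic events in the reduction arm would be an artefact, only that the plan as written could not tell.

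**What to change.** - **Study Procedures 3.e.ix and Table 2:** record a glucose value at each study draw already scheduled, in both arms, from the BMP, point-of-care or other sources already allowed. Leave clinically triggered testing unchanged. State that a triggered reading does not replace the scheduled one under the substitution rule in 3.e.ii, since that would bring the arm-dependent trigger back in.
- **Statistical Considerations:** keep the Table 3 adverse-event tabulation on all glucose values. Add a between-arm comparison of the scheduled values, for example in the mixed models already planned for repeated continuous measures. Report the number of glucose measurements per infant or per PN-day beside the glycaemic event rates.

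The cost is one table row, two or three sentences, and a drop of blood or an added assay at existing draws, with the Table 2 blood volumes updated if needed. Single scheduled readings cannot by themselves meet the repeat-determination grades and will miss brief excursions. They supplement the adverse-event comparison and do not replace it.
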